6.15.5. Vital Signs and Other Physical Findings

Vital signs and physical characteristics will be summarized and analyzed for the following periods:

- Open-Label Treatment Period (Safety Population)
- Post-Treatment Follow-up Period (Post-Treatment Follow-Up Population)

For vital signs and physical characteristics, the observed values at each visit (starting at baseline) and change from baseline to each scheduled visit, respectively, will be displayed in box plots for patients who have both baseline and at least 1 post-baseline result. Baseline will be the last nonmissing observation in the baseline period. Original-scale data will be used for the display. Unscheduled visits and repeat measurements will be excluded. Reference limits will not be displayed. The following summary statistics will be included in a table below the box plot: N, mean, standard deviation, minimum, Q1, median, Q3, and maximum. P-values and confidence limits will not be included in the summary statistics at the bottom of the box plot. Box plots will be used to evaluate trends over time and to assess a potential impact of outliers on central tendency summaries.

The frequency and percentages of patients with treatment-emergent high or low vital signs and physical characteristics results at any time will be summarized by treatment group for Period 2 and Period 3, respectively.

- A treatment-emergent **high** result is defined as a change from a value less than or equal to the high limit at all baseline visits to a value greater than the high limit at any time that meets the specified change criteria during the treatment period.
- A treatment-emergent **low** result is defined as a change from a value greater than or equal to the low limit at all baseline visits to a value less than the low limit at any time that meets the specified change criteria during the treatment period.

[Table RHCF.6.8](#) will be used to define the low and high baseline values as well as the limits that are specified as treatment emergent. Note: Weight does not have an abnormal baseline; therefore, the treatment-emergent values are determined by change from baseline. For categorical variables, scheduled visits, unscheduled visits, and repeat measurements will be included.

Table RHCF.6.8. Categorical Criteria for Abnormal Treatment-Emergent Blood Pressure and Pulse Measurement, and Categorical Criteria for Weight and Changes for Adults

Parameter	Low	High
Systolic BP (mm Hg) ¹ (supine or sitting – forearm at heart level)	≤90 and decrease from baseline ≥20	≥140 and increase from baseline ≥20
Diastolic BP (mm Hg) ¹ (supine or sitting – forearm at heart level)	≤50 and decrease from baseline ≥10	≥90 and increase from baseline ≥10
Pulse (bpm) ¹ (supine or sitting)	<50 and decrease from baseline ≥15	>100 and increase from baseline ≥15
Weight (kg)	(Loss) decrease from baseline ≥7%	(Gain) increase from baseline ≥7%

Abbreviations: BP = blood pressure; bpm = beats per minute.

¹ Baseline abnormal values are defined by the value presented.

6.15.6. Columbia-Suicide Severity Rating Scale

The Columbia-Suicide Severity Rating Scale (C-SSRS) is an assessment tool that evaluates suicidal ideation and behavior. Information on the C-SSRS scale can be found through the following link: <http://www.cssrs.columbia.edu>.

Specifically, the following outcomes are C-SSRS categories and have binary responses (yes/no). The categories have been re-ordered from the actual scale to facilitate the definitions of the composite and comparative endpoints and to enable clarity in the presentation of the results.

Category 1 – Wish to be Dead

Category 2 – Non-specific Active Suicidal Thoughts

Category 3 – Active Suicidal Ideation with Any Methods (Not Plan) without Intent to Act

Category 4 – Active Suicidal Ideation with Some Intent to Act, without Specific Plan

Category 5 – Active Suicidal Ideation with Specific Plan and Intent

Category 6 – Preparatory Acts or Behavior

Category 7 – Aborted Attempt

Category 8 – Interrupted Attempt

Category 9 – Actual Attempt (non-fatal)

Category 10 – Completed Suicide.

Self-injurious behavior without suicidal intent is also a C-SSRS outcome (although not suicide related) and has a binary response (yes/no).

Composite endpoints based on the above categories are defined below.

- **Suicidal ideation:** A “yes” answer at any time during treatment to any 1 of the 5 suicidal ideation questions (Categories 1-5) on the C-SSRS.
- **Suicidal behavior:** A “yes” answer at any time during treatment to any 1 of the 5 suicidal behavior questions (Categories 6-10) on the C-SSRS.

- **Suicidal ideation or behavior:** A “yes” answer at any time during treatment to any 1 of the 10 suicidal ideation and behavior questions (Categories 1-10) on the C-SSRS.

The Self-Harm Supplement Form is a 1-question form that is completed, at any visit, including baseline visit, that asks for the number of suicidal behaviors, possible suicidal behaviors, or nonsuicidal self-injurious behaviors the patient has experienced since the last assessment. For each unique event identified, a questionnaire (Self-Harm Follow-Up Form) that collects supplemental information on the self-injurious behavior is to be completed.

Change from baseline to each post-baseline visit in C-SSRS total score will be analyzed using MMRM methods for the safety population during Period 2. If the number of patients in analysis is less than 10% of patients in total, only a by-patient listing will be provided.

The C-SSRS will be listed by patient and visit. Only patients that show suicidal ideation/behavior or self-injurious behavior without suicidal intent will be displayed (that is, if a patient’s answers are all “no” for the C-SSRS, then that patient will not be displayed). However, if a patient reported any suicidal ideation/behavior or self-injurious behavior without suicidal intent at any time point, then all ideation and behavior for that patient will be displayed, even if not positive. Note, missing data should not be imputed.

The Self-Harm data will be listed by patient and visit if number of events on Self-Harm Supplement Form is not zero in the CRF “*Self-Harm Questionnaire Supplement.*”

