10.3.4.3. Vital Signs, Physical Findings, and Other Safety Evaluations

Vital signs will be analyzed as mean changes from baseline and as incidence of abnormal values and will be summarized for both predose and postdose at Week 0 (Week 2) and Week 52 (Visit 11), as applicable.

Suicide-related thoughts and behaviors and self-injurious behavior with no suicidal intent, based on the C-SSRS, will be listed by patient.

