6.15. Safety Analyses

The primary safety analyses will focus on comparisons of ixekizumab versus adalimumab in the Open-Label Treatment Period (Period 2). Fisher's exact test will be used for all AEs and other categorical safety data. Continuous vital sign and laboratory values will be analyzed by an ANCOVA with treatment and baseline value in the model. Type 3 sums of squares will be used. The significance of within-treatment group changes from baseline will be evaluated by testing whether the treatment group LSMeans changes from baseline are different from zero using a t-statistic. In addition to the LSMeans and tests, the standard deviation, minimum, median, and maximum will be displayed. Unless otherwise specified, change from baseline will include only those subjects with both baseline and post-baseline measures.

For safety analyses, p-values should be interpreted with caution as the analyses are intended to be descriptive and should not be thought of as hypothesis testing, unless there is a prespecified hypothesis. P-values and CIs, if reported, provide some evidence of the strength of the finding and are only useful as a flagging mechanism.

Summaries of safety data collected during the Post-Treatment Follow-Up Period will be presented separately. The categorical safety measures will be summarized with incidence rates. The continuous safety measures will be summarized using mean changes.

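### SAP 6.15.6 plans an MMRM on a C-SSRS total score that neither document defines, although the C-SSRS outcomes it does define are all yes/no

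*SAP*

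**What the plan says.** SAP 6.15.6 introduces the scale by stating that "the following outcomes are C-SSRS categories and have binary responses (yes/no"). It lists ten categories: five of ideation and five of behaviour. It adds a separate yes/no item for self-injury without suicidal intent. Three composites follow: ideation (Categories 1 to 5), behaviour (6 to 10), and either. Each counts a patient once if there is a yes during treatment, the widest being a yes "to any 1 of the 10 suicidal ideation and behavior questions (Categories 1-10) on the C-SSRS".

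The planned comparison then uses a different variable. Change from baseline to each later visit in "C-SSRS total score will be analyzed using MMRM methods for the safety population during Period 2". The next sentence is a fallback: "If the number of patients in analysis is less than 10% of patients in total, only a by-patient listing will be provided". Separately, "The C-SSRS will be listed by patient and visit", restricted to patients who show ideation, behaviour or self-injury.

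Three other places bear on this:

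- SAP 6.15 sets the general safety rule: Fisher's "exact test will be used for all AEs and other categorical safety data".
- Protocol 10.3.4.3 plans no model and no score. Suicide-related thoughts and behaviours, "based on the C-SSRS, will be listed by patient".
- The objectives tables (Table RHCF.4.1 in both documents) give change from baseline in C-SSRS as the only entry under Safety, without naming a score.

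**The concern.** A programmer needs to know which items enter a score, their weights, the range and the rule for missing items. None of this is given. If the rule is chosen once data are available, that choice can settle whether a given patient counts as better or worse.

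The method is also a poor match. SAP 6.2.2 specifies the MMRM for continuous efficacy and health outcome variables. SAP 6.15 uses ANCOVA for continuous vital sign and laboratory values and Fisher's exact test for categorical safety data. The composites are single yes/no results over the treatment period, so they have no value at each visit and no change from baseline to model.

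At stake is the usefulness of the C-SSRS comparison between arms, in a trial that has no data monitoring committee (Protocol 10.3.7, SAP 6.18). The clear summary would be how many patients in each arm had ideation or behaviour. Section 6.15.6 builds the composites for it but names no analysis of them.

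**Working it through.** The documents state no figure to reproduce. The check has three parts.

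**1. Is there a scoring rule anywhere?** SAP 6.15.6 gives yes/no items and composites only. SAP Tables RHCF.6.3 and RHCF.6.5, which hold the derivations for efficacy and health outcomes, do not cover the C-SSRS, and no SAP appendix does. Protocol 9.4.3 describes the instrument and its administration without a score. The total score is therefore undefined.

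**2. Does the missing rule matter?** Four rules that an analyst might adopt are applied to the ten SAP categories. The rules and patients are illustrations and do not come from the documents. Change = score after baseline minus score at baseline.

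| Illustrative patient | Number of yes answers | Highest category | Sum of category numbers | Highest ideation category (1 to 5) |
|---|---|---|---|---|
| Baseline {1}; later {1, 2, 3} | 3 - 1 = +2 | 3 - 1 = +2 | 6 - 1 = +5 | 3 - 1 = +2 |
| Baseline none; later {9} | 1 - 0 = +1 | 9 - 0 = +9 | 9 - 0 = +9 | 0 - 0 = 0 |
| Baseline {1, 2, 3}; later {6} | 1 - 3 = -2 | 6 - 3 = +3 | 6 - 6 = 0 | 0 - 3 = -3 |

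For the second patient, an actual attempt is worth 0, 1 or 9 points. For the third, the rules disagree on the sign.

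**3. When does the listing-only clause apply?** The planned number is 550 (SAP 5.2), so the threshold is 0.10 x 550 = 55 patients.

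- *Reading A: everyone with C-SSRS data is in the analysis.* The Schedule of Activities places the scale at screening, baseline and all eight post-baseline clinic visits (Visits 4 to 11). Nearly all 550 would count, the clause would not apply, and the undefined MMRM would be required.
- *Reading B: only patients with a positive answer are in the analysis.* The clause applies when fewer than 55 patients are positive. With X ~ Binomial(550, p), the chance is P(X < 55). The documents give no prevalence, so p is an assumption:

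| Assumed p | Expected positives, 550p | P(X < 55) |
|---|---|---|
| 5% | 27.5 | about 1.00 |
| 8% | 44 | 0.95 |
| 10% | 55 | 0.48 |
| 12% | 66 | 0.06 |

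The same sentence can thus require the model or remove it, depending on an undefined phrase.

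**The case against.** The strongest reply is that little is lost. The C-SSRS and self-harm listings can be produced. SAP Table RHCF.6.7 summarises depression and suicide/self-injury events by preferred term within a standardised MedDRA query, and that query, not the C-SSRS, defines the adverse event of special interest. The composites are categorical safety data, so the Fisher rule in SAP 6.15 can be read to cover them. The protocol promises only a listing. SAP 6.15 itself treats safety p-values as descriptive. All of this stands, and it limits the point to one analysis.

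Three stronger readings are tempting, and the documents do not support them:

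- *A reader might infer that arms cannot be compared on suicidality at all, or that the composites get no comparison.* The event summary and the general Fisher rule contradict this. What is missing is a named analysis of the composites in 6.15.6.
- *A reader might infer that the fallback could never apply.* That holds only on Reading A. Reading B has support: the listing is itself confined to patients with a positive response, and Reading A leaves the clause almost no work to do. The wording settles neither.
- *A reader might infer that the score would be almost all zeros.* Exclusion criterion 31, which screens out recent attempts and higher-level ideation, makes few positives plausible. Neither document gives a rate, so this remains an assumption.

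The reply does not supply a definition of the score, and it does not make an MMRM suitable for yes/no items.

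**Conclusion.** The point holds in a limited form. The MMRM in SAP 6.15.6 rests on an undefined variable, cannot be programmed as written, and does not fit the yes/no outcomes that the section defines. The 10% clause is ambiguous, with a threshold of 55 of 550 on one reading and practically no effect on the other. The section should also say how its composites are analysed and not leave this to a general rule elsewhere.

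The definitional finding needs no assumption. The scoring illustrations assume four possible rules, and the fallback probabilities assume a prevalence and independence between patients. The effect is confined to one descriptive safety analysis. The primary and major secondary tests, the type I error control and the sample size are untouched. It should be corrected because the endpoint wording, the protocol's listing and the SAP's model do not agree, and a simpler method is already at hand.

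**What to change.** In SAP 6.15.6:

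1. Delete the total-score MMRM and the 10% clause attached to it.
2. State that the number and percentage of patients with on-treatment suicidal ideation, suicidal behaviour, either of these, and self-injury without suicidal intent will be tabulated by arm for the safety population in Period 2, and compared with Fisher's exact test under SAP 6.15.
3. Keep the listing by patient and visit.
4. State that these summaries address the endpoint of change from baseline in C-SSRS.

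The cost is a few sentences of SAP text. The data are already collected, the outcomes are already defined, and the tables are less work than the model. The wording is best fixed before anyone tabulates C-SSRS results by arm. The endpoint also appears in the protocol synopsis and Protocol Table RHCF.4.1. Rewording it there is optional and can wait for the next amendment.

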6.15.7. Immunogenicity

Not applicable.

6.15.8. Electrocardiograms

Not applicable.

6.16. Subgroup Analyses

6.16.1. Safety Subgroup Analyses

Safety subgroup analysis for common TEAEs and AESIs of allergy/hypersensitivity, infections, and injection site reactions will be summarized by treatment and overall, during the Open-Label Treatment Period for the safety population.

Subgroups to be evaluated include the following:

- Patient Demographic Subgroups:
 - Sex: female or male
 - Age group: <65 years, or ≥65 years
- Geographic Region Subgroups:
 - Geographic region: Europe, Rest of the World
- Concomitant Therapy:
 - Concomitant csDMARD use at baseline: yes or no
 - Concomitant methotrexate use at baseline: yes or no

- Concomitant glucocorticoids use at baseline: yes or no
- Baseline Severity Groups:
 - Moderate-to-severe plaque psoriasis involvement: yes or no

Treatment effects will be assessed within the subgroups using the Fisher's exact test. The most common TEAEs and AESI will be presented by MedDRA PT nested within SOC (SMQ or High Level Term where specified). A logistic regression model will be used to test the treatment-by-subgroup interaction. The response variable will be each AE. The explanatory variables will be treatment, subgroup, and treatment by-subgroup interaction. The interaction test will be evaluated at the 0.10 significance level. If any of the subgroups (for example, the age <65 group or the age ≥65 group) is less than 10% of the total population, only descriptive statistics will be provided for that subgroup (that is, no inferential testing).

6.16.2. Efficacy Subgroup Analyses

Subgroup analyses will be conducted for the following efficacy assessments:

- ACR50 and PASI 100 simultaneous response rate at Week 24 with ITT Population in the Open-Label Treatment Period

Subgroups to be evaluated include the following:

- Patient Demographic Subgroups:
 - Age group: <65 years or ≥65 years
 - Ethnicity: Hispanic or Latino, Non-Hispanic and Non-Latino
- Geographic Region Subgroups:
 - Geographic region: Europe, Rest of the World
- Concomitant Therapy:
 - Concomitant csDMARD use at baseline: yes or no
 - Concomitant methotrexate use at baseline: yes or no
 - Concomitant glucocorticoids use at baseline: yes or no
 - Number of prior csDMARD therapies: 1, 2, 3, or >3
- Baseline Severity Groups:
 - Moderate-to-severe plaque psoriasis involvement: yes or no

Additional exploratory subgroup analyses will be conducted for the following efficacy assessments:

- ACR20, 50, and 70 response rates at Week 24 with ITT population in the Open-Label Treatment Period
- PASI 75, 90, and 100 response rates at Week 24 with ITT population in the Open-Label Treatment Period

Subgroup to be evaluated includes:

- Concomitant Therapy:
 - Concomitant csDMARD use at baseline: yes or no
 - Concomitant methotrexate use at baseline: yes or no

- Baseline Severity Groups:
 - Moderate-to-severe plaque psoriasis involvement: yes or no

A logistic regression model with treatment, subgroup, and the interaction of treatment-by-subgroup included as factors will be used. The treatment-by-subgroup interaction will be tested at the significance level of 0.10. Treatment group effects will be evaluated within each category of the subgroup using Fisher's exact test, regardless of whether the interaction is statistically significant. Missing data will be imputed using NRI, as described in Section 6.4.1. The treatment differences with 95% CIs by each subgroup category will be reported. If any of the subgroups (for example, the age <65 group or the age ≥65 group) is less than 10% of the total population, only descriptive statistics will be provided for that subgroup (that is, no inferential testing).

6.17. Protocol Violations

Protocol deviations will be identified throughout the study. Important protocol deviations are defined as those violations from the protocol likely to have a significant impact on the completeness, accuracy, and/or reliability of the study data or that may significantly affect a subject's rights, safety, or well-being.

[Table RHCF.6.9](#) includes the categories and subcategories of important protocol violations, the source of identification for the violation, and the statistical programming guidance for the CSR.

A by-patient listing of important protocol deviations will be provided for all entered patients.

The number and percentage of patients having important protocol violation(s) will be summarized within category and subcategory of violations by treatment group for the following:

- Open-Label Treatment Period (ITT Population)

Additional analyses will be conducted on patients who don't have any or a subset of protocol violations for primary and/or major secondary endpoints.

Table RHCF.6.9. Identification and Action of Important Protocol Violations

Important Protocol Violation Category/Subcategory	Source to Identify Protocol Violation	Statistical Programming Guidance for Clinical Study Report
Category: Informed Consent		
Sub-Category: Informed Consent not Obtained/Missing/Late	Monitor and Stats	Either from monitor’s list, or, If patient informed consent date is after Visit 1 date or missing informed consent
Subcategory: Improper Informed Consent	Monitor	Monitor’s list
Category: Eligibility		
[1] Age <18 years	Monitor	Monitor’s list
[1a] Male patients disagree to use a reliable method of birth control during the study.	Monitor	Monitor’s list: male patients who disagree to use a reliable method of birth control during the study.
[1b] Pregnancy confirmation at Visit 1 and prior to randomization at Visit 2.	Monitor	Monitor’s list: positive pregnancy test result from lab test at Visit 1, and check if patient was randomized and takes drug. Check Visit 2 urine pregnancy test.
[1b] Are women ≥40 and <60 years of age who have had a cessation of menses for at least 12 months, and FSH <40 mIU/mL	Monitor and Stats	Monitor’s list: Women ≥40 and <60 years of age who do not have negative bHCG results and who have a FSH <40 mIU/mL at Visit 1.
[1b] Are women of non-childbearing potential, defined as either women who have had surgical sterilization or who are ≥60 years of age	Monitor	Monitor’s list: women who have had surgical sterilization.
[2] No confirmed diagnosis of PSA of at least 6 months prior to baseline or did not meet CASPAR criteria	Monitor	Monitor’s list
[3] <3 TJC or <3 SJC at Visit 1 or 2	Monitor	Monitor’s list.
[4] BSA <3% at Visit 1 or 2	Monitor and Stats	Monitor’s list. Check if BSA <3% either at Visit 1 or at Visit 2
[50] Have not been treated with 1 or more csDMARDs	Monitor and Stats	Monitor’s list and stats programming. Check past or present use for MTX, sulfasalazine, leflunomide, or hydroxychloroquine

Important Protocol Violation Category/Subcategory	Source to Identify Protocol Violation	Statistical Programming Guidance for Clinical Study Report
[6] Currently enrolled in any other clinical trial involving an investigational product or any other type of medical research judged not to be scientifically or medically compatible with this study	Monitor	Monitor’s list.
[7] Have received prior or currently receiving treatment with any biologic or small molecule therapy for PsA or Ps, including investigation therapies (such as, but not limited to, a TNF inhibitor, IL-1 receptor antagonists, IL-6 inhibitor; anti-IL-12/23p40, T cell or B cell targeted therapies, or Janus kinase inhibitors). Note: previous treatment of phosphodiesterase type 4 inhibitors will be permitted. Treatment with phosphodiesterase type 4 inhibitors must have been discontinued at least 8 weeks before randomization (Visit 2).	Monitor	Monitor’s list
[8] Previous or current medication exposure at Visit 1 to LY2439821 or IL-17 antagonists or previous participation in the current study. (Note: See protocol for patients who may be allowed to re-screen.)	Monitor	Monitor’s list
[9] Have history of drug-induced Ps.	Monitor	Monitor’s list
[10] Use of csDMARDs (other than MTX, leflunomide, sulfasalazine, or cyclosporine) within 8 weeks prior to Visit 2; or have discontinued MTX, leflunomide, sulfasalazine, or cyclosporine within 12 weeks prior to Visit 2.	Monitor	Monitor’s list
[11] Have discontinued leflunomide within 4 weeks prior to Visit 2 or from 4 to 12 weeks prior without drug elimination procedure.	Monitor and Stats	Monitor’s list, or, If the difference between Visit 2 date and medication end date <28 days for previous therapy, Leflunomide
[12] Use of oral corticosteroids at average daily doses of >10 mg/day of prednisone or equivalent, use of variable doses within 4 weeks prior to Visit 2.	Monitor	Monitor’s list

Important Protocol Violation Category/Subcategory	Source to Identify Protocol Violation	Statistical Programming Guidance for Clinical Study Report
[13] Have received parenteral glucocorticoids within 6 weeks prior to Visit 2 or if use is anticipated during the first 24 weeks of open-label treatment period (Period 2) of the study	Monitor and Stats	Monitor’s list, or, If a patient has a reported previous therapy of parenteral glucocorticoids with and either a start or end date <42 days prior to the Visit 2 date
[14] Concomitant use of NSAIDs or cyclooxygenase - 2 inhibitors unless on a stable dose for at least 2 weeks prior to Visit 2	Monitor	Monitor’s list
[15] Use of opiate analgesics at average daily doses of >30 mg/day of morphine or equivalent or variable doses within 6 weeks prior to Visit 2	Monitor and Stats	Monitor’s list, or, If a patient has either a reported previous therapy of opiate analgesics with average dose >30 mg/day or a concomitant medication with ATC codes of N02AA with a start or end date of <42 days prior to Visit 2 date.
[16] Have received systemic nonbiologic Ps therapy other than csDMARDs or corticosteroids as indicated above (including, but not limited to oral psoralens and ultraviolet A light therapy oral retinoids, thioguanine, hydroxyurea, sirolimus, azathioprine, fumaric acid derivatives, or 1, 25 dihydroxy vitamin D3 and analogs) or phototherapy (including either oral and topical ultraviolet A, ultraviolet B, or self-treatment with tanning beds or therapeutic sunbathing) within 4 weeks prior to randomization (Visit 2); or had topical Ps treatment within the previous 2 weeks prior to randomization (Visit 2). Note WHO Group 1 weak potency topical steroids are allowed.	Monitor and Stats	Monitor’s list, or, If the patient has any record with a start date or an end date <28 days of the Visit 2 date for phototherapy for previous therapy. If the patient has any concomitant medications with a start date or an end date that is on or prior to Visit 2 date, and <28 days prior to the Visit 2 date for oral medications. If the patient has any concomitant medications with an end date that is on or prior to Visit 2 date, and ≤14 days prior to the Visit 2 date for topical medications. Note: ATC codes will be provided by medical in a separate file.
[17] Use of tanning booths for at least 4 weeks prior to Visit 2 and during the study for patients with plaque psoriasis.	Monitor	Monitor’s list
[18] Have a known allergy or hypersensitivity to any biologic therapy that would pose an unacceptable risk to the patient if participating in this study.	Monitor	Monitor’s list

Important Protocol Violation Category/Subcategory	Source to Identify Protocol Violation	Statistical Programming Guidance for Clinical Study Report
[19] Ever received efalizumab or natalizumab or other agents that target alpha-4-integrin	Monitor	Monitor’s list
[20] Have been exposed to a live vaccine within 12 weeks prior to Visit 2 or intend to have a live vaccination during the course of the study, or within 12 weeks of completing treatment in this study, or participated in other vaccine clinical study within 12 weeks prior to Visit 2	Monitor	Monitor’s list
[21] Had a BCG (12 months prior to Visit 2), or intent to have this vaccine with BCG during the study or within 12 months of completion of the study	Monitor	Monitor’s list
[22] Have diagnosis of other inflammatory arthritic syndrome	Monitor	Monitor’s list
[23] Have active Crohn's disease or active ulcerative colitis	Monitor	Monitor’s list
[24] Have current diagnosis of fibromyalgia or other chronic pain condition that would confound evaluation of the patient	Monitor	Monitor’s list
[25] Evidence of active vasculitis or uveitis	Monitor	Monitor’s list
[26] Surgical treatment of joint within 8 weeks prior to Visit 2 or will require such up to Week 24	Monitor	Monitor’s list
[27] Had any major surgery within 8 weeks prior to Visit 2, or will require such during the study that, in the opinion of the investigator in consultation with Lilly or its designee, would pose an unacceptable risk to the patient.	Monitor	Monitor’s list
[28] Have active or history of malignant disease within the 5 years prior to Visit 2. Note: Patients with successfully treated basal-cell carcinoma (no more than 3), squamous-cell carcinoma of the skin (no more than 2), within the 5 years prior to Visit 2 may participate in the study.	Monitor	Monitor’s list

Important Protocol Violation Category/Subcategory	Source to Identify Protocol Violation	Statistical Programming Guidance for Clinical Study Report
[29] Presence of significant uncontrolled cerebro-cardiovascular (for example, MI, unstable angina, unstable arterial hypertension, moderate-to-severe NYHA class III/IV heart failure, or CVA), respiratory, hepatic, renal, gastrointestinal, endocrine, hematologic, neurologic, or neuropsychiatric disorders, or abnormal laboratory values, or illicit drug use (including cannabinoids, whether legalized or not) at screening that in the opinion of the investigator pose an unacceptable risk to the patient if participating in the study or of interfering with the interpretation of data.	Monitor	Monitor’s list
[30] Have had uncompensated heart failure, fluid overload, or MI, or evidence of new-onset ischemic heart disease or other serious cardiac disease within 12 weeks prior to Visit 2.	Monitor	Monitor’s list
[31] Presence of significant uncontrolled neuropsychiatric disorder; have recent history (within 30 days prior to screening visit (Visit 1) and any time between screening visit (Visit 1) and randomization (Visit 2) of a suicide attempt; or develops active suicidal ideation with some intent to act with or without a specific plan (yes to question 4 or 5 on the “Suicidal Ideation” portion of the C-SSRS) or develops suicide-related behaviors as recorded on the C-SSRS at screening or randomization (Visit 2); or are clinically judged by the investigator to be at risk for suicide.	Monitor and Stats	Monitor’s list, or, If a patient has a yes to question 4 or 5 on the “Suicidal Ideation” portion of the C-SSRS or develops suicide-related behaviors as recorded on the C-SSRS at Visits 1 or 2.
[32] Have presence or personal history or family history (first degree relative) of demyelinating disorder.	Monitor	Monitor’s list

Important Protocol Violation Category/Subcategory	Source to Identify Protocol Violation	Statistical Programming Guidance for Clinical Study Report
[33] Have serious infection, been hospitalized, received IV antibiotics for an infection within 12 weeks of Visit 2, or had a serious bone or joint infection within 24 weeks prior to Visit 2, or have ever had an infection of an artificial joint, or an infection that occurs with increased incidence in an immunocompromised host (including, but not limited to, Pneumocystis jirovecii pneumonia, active histoplasmosis, or coccidioidomycosis), or have a known immunodeficiency.	Monitor	Monitor's list
[34] Have a known immunodeficiency or are immunocompromised to an extent such that participation in the study would pose an unacceptable risk to the patient.	Monitor	Monitor's list
[35] Have or had a herpes zoster or any other clinically apparent varicella-zoster virus infection within 12 weeks prior to Visit 2.	Monitor	Monitor's list
[36] Evidence or suspicion of active or latent TB (refer to RHCF Protocol Section 9.4.4.2 for details on determining full TB exclusion criteria).	Monitor	Monitor's list
[37] Have any other active or recent infection other than mentioned above within 4 weeks of randomization (Visit 2) that, in the opinion of the investigator, would pose an unacceptable risk to the patient if participating in the study. Note: These patients may be rescreened once ≥ 4 weeks after documented resolution of symptoms	Monitor	Monitor's list
[38] Sitting systolic blood pressure >160 mm Hg or diastolic blood pressure >100 mm Hg. Note: Determined by 2 consecutive elevated readings.	Monitor and Stats	Monitor's list, or, If a patient's systolic blood pressure >160 mm Hg or diastolic blood pressure >100 mm Hg at Visit 2 (pre-dose read)

Important Protocol Violation Category/Subcategory	Source to Identify Protocol Violation	Statistical Programming Guidance for Clinical Study Report
[39] Are positive for HIV serology (positive for HIV antibody)	Monitor and Stats	Monitor’s list, or, If a patients laboratory tests at Visit 1 indicate they are positive for HIV antibody
[40] Have evidence of or test positive for hepatitis B by any of the following criteria: 1) positive for hepatitis B surface antigen (HBsAg+); 2) positive for anti-hepatitis B core antibody (HBcAb+) and positive for HBV DNA. Note: Patients who are HBsAg-, and HBcAb+ and HBV DNA negative may be enrolled in the study. Patients who meet these criteria at screening will be identified by the central laboratory and monitored during the study as detailed in Section 9.4.5.4 of the RHCF protocol.	Monitor and Stats	Monitor’s list; or If test positive for HBV at Visit 1 by testing: 1) positive for hepatitis B surface antigen (HBsAg+), OR 2) positive for anti-hepatitis B core antibody (HBcAb+) AND are HBV DNA positive. Note: If multiple records at Visit 1, use the last observation. Patients who are HBsAg- AND HBcAb+ AND HBV DNA negative can be enrolled. This would not be a protocol violation.
[41] Have evidence of or test positive for HCV. A positive test for HCV is defined as: 1) positive for hepatitis C antibody (anti-HCV Ab), and 2) positive via a confirmatory test for HCV (for example, HCV polymerase chain reaction).	Monitor and Stats	Monitor’s list, or, If a patient’s laboratory tests at Visit 1 indicate they are positive for HCV.

Important Protocol Violation Category/Subcategory	Source to Identify Protocol Violation	Statistical Programming Guidance for Clinical Study Report

[42] The most recent lab panel meet any of the following criteria: [42a] Neutrophil count <1500 cells/μL [42b] Lymphocyte count <800 cells/μL [42c] Platelet count <100,000 cells/μL [42d] AST or ALT >2.5\times ULN [42e] Total WBC count <3000 cells/μL [42f] Hemoglobin <8.5 g/dL (85.0 g/L) for male patients and <8.0 g/dL (80 g/L) for female patients [42g] Serum creatinine >2.0 mg/dL. [42h] Have clinical laboratory test results at screening that are outside the normal reference range for the population and are considered clinically significant, per investigator assessment. Note: Laboratory tests can be repeated a maximum of 1 time, and results must be received and reviewed prior to randomization (Visit 2).
	
Monitor and Stats
	
Monitor’s list, or, If a patients laboratory tests at Visit 1 indicate any of the following: Neutrophil count <1500 cells/μL Lymphocyte count <800 cells/μL Platelet count <100,000 cells/μL AST or ALT >2.5\times ULN Total WBC <3000 cells/μL Hemoglobin <8.5 g/dL for male patients and <8 g/dL for female patients Serum creatinine >2 mg/dL

[43] Have any condition or contraindication as addressed in the local labelling for adalimumab that would preclude the patient from participating in this protocol.
	
Monitor
	
Monitor’s list

[44] Have any other condition that precludes the patient from following and completing the protocol.
	
Monitor
	
Monitor’s list

[45] Are women who are breastfeeding
	
Monitor
	
Monitor’s list

[46] Are study site personnel directly affiliated with this study and/or their immediate families. Immediate family is defined as a spouse, parent, child, or sibling, whether biological or legally adopted.
	
Monitor
	
Monitor’s list

[47] Are Lilly employees or its designee or are employees of third-party organizations involved in the study.
	
Monitor
	
Monitor’s list

Important Protocol Violation Category/Subcategory	Source to Identify Protocol Violation	Statistical Programming Guidance for Clinical Study Report
[48] Are currently enrolled in, or discontinued from a clinical trial involving an investigational product or nonapproved use of a drug or device within the last 4 weeks or a period of at least 5 half-lives of the last administration of the drug, whichever is longer, or are concurrently enrolled in any other type of medical research judged not to be scientifically or medically compatible with this study.	Monitor	Monitor's list
[49] Are unwilling or unable to comply with the use of a data collection device to directly record data from the patient.	Monitor	Monitor's list
Category: Study Procedures		
Sub-Category: Violation of Discontinuation Criteria		
[D1] Discontinuation of the study drug after consultation with medical monitor for abnormal liver tests, defined as having 1 of the following: ALT or AST >8× ULN ALT or AST >5× ULN for more than 2 weeks ALT or AST >3× ULN and total bilirubin level >2× ULN or prothrombin time >1.5× ULN ALT or AST >3×ULN with the appearance of fatigue, nausea, vomiting, right upper-quadrant pain or tenderness, fever, rash, and/or eosinophilia (>5%) ALP >3× ULN ALP >2.5× ULN and TBL >2× ULN ALP >2.5× ULN with the appearance of fatigue, nausea, vomiting, right quadrant pain or tenderness, fever, rash, and/or eosinophilia (>5%)	Monitor	Monitor's list

Important Protocol Violation Category/Subcategory	Source to Identify Protocol Violation	Statistical Programming Guidance for Clinical Study Report
[D2] Neutrophil (segmented) counts: <500 cells/ μ L; or \geq 500 and <1000 cells/ μ L (from 2 test results; the second test must be performed within 1 week from knowledge of the initial result); or \geq 1000 and <1500 cells/ μ L (from 3 test results) and an infection that is not fully resolved	Monitor and Stats	Monitor’s list, or, If a patient still receives study treatment after 10 days of latest dose with confirmed segmented neutrophil counts <500 cells/ μ L; \geq 500 and <1000 cells/ μ L (from a test and a re-test result; the re-test must be performed within 1 week from knowledge of the initial result); or \geq 1000 and <1500 cells/ μ L (from a test and 2 re-test results) and an infection that is not fully resolved If there are missing re-test results, use the non-missing results
